In the initial safety cohort, a minimum of 3 patients will be treated at the SBRT dose of 30Gy in 3 fractions combined with pembrolizumab. The gap left between the treatments of each subsequent patient will start after the second cycle of Pembrolizumab in the previous dosed patient to mitigate against multiple patients suffering from acute toxicity. The DLT period for this study is 12 weeks from the last dose of SBRT (i.e. at C6D1). Patients included in Part A will be considered by the Safety Review Committee (SRC) once the 3rd and 6th patient in the Part A cohort has completed the DLT period. If 0 out of 3 patients experience a DLT, or if 1 out of 3 patients experience a DLT in Part A, then the cohort will be expanded to 6 patients. If 1 in 6 patients experience a DLT, then it will be acceptable to move forward to the expansion cohort (Part B). However, if ≥ 2 in 6 patients (or more than 1 in the first 3 patients) experience a DLT then the maximum administered dose

(MAD) will have been reached. If the MAD is seen at a dose level of 30 Gy in 3# then the study will be terminated.

While waiting for 3 or 6 patients to complete the DLT period, no additional patients will be recruited. Further patients can only be recruited after the SRC has reviewed the toxicity data for the cohort to proceed to Part B. Patients obtaining complete response or having completed 35 cycles of pembrolizumab must discontinue and may recommence for additional 17 cycles upon subsequent disease, the CI/PI will need to discuss with the sponsor and MSD, on a case by case basis for the continuation of pembrolizumab.

Table 1: SBRT dose level and pembrolizumab dosing during the initial safety cohort and expansion phase.

Dose Level	Pembrolizumab Dose	SBRT to part of a MPM lesion
Initial safety cohort	200 mg i.v. over 30 minutes, every 3 weeks	30 Gy in 3# (Monday, Wednesday, Friday)
Expansion cohort	200 mg i.v. over 30 minutes, every 3 weeks	30 Gy in 3# (Monday, Wednesday, Friday)

SBRT: Stereotactic Ablative Body Radiotherapy; Gy: Gray; i.v.: intravenous; mg: milligrams; #: fraction.

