12.3 Appendix 3 – Radiotherapy Planning and Delivery Guidelines

Positioning and Immobilisation

- Patients will be supine and positioned to aid comfort, stability and setup reproducibility. Knee and / or ankle supports will be used.
- For the majority of patients, the arms will be positioned above the head using a chest board and consideration will be given to using a vacuum bag to aid comfort and stability, particularly for treatment of vertebral lesions.
- For patients with apical target lesions, the arms may be positioned by their sides and the patient immobilised in a 5-point shell.

Localisation Imaging

- Respiratory correlated 4DCT
- Maximum slice thickness will be 3 mm.
- The extent of the scan is from above the cricoid to below the liver.
- IV contrast will be considered, unless medically contraindicated, where it will aid target delineation e.g. contouring of brachial plexus avoidance structure using vessels as a surrogate.

Target Delineation

- GTV = Radiologically visible peripheral pleural lesion or part of a lesion up to 3 cm and no greater than 5 cm in diameter, not in a ‘central’ location (See Figure A below). Ideally this should be in as thick an area of MPM as possible. GTV will be a minimum of 2 cm in one direction (SUP/INF, ANT/POST, LAT) and no less than 1 cm in any direction.
- CTV = GTV. No additional margin is added for microscopic disease.
- ITV = Encompasses either the CTV at maximum inhale and maximum exhale generated by fusing the individual GTV from 4DCT dataset.
- PTV = ITV + 5 mm.

Organ at Risk Delineation

- See Table A below.
- Additional guidance can be found in the online Radiation Therapy Oncology Group (RTOG) normal tissue atlases, available at: <https://www.rtog.org/CoreLab/ContouringAtlases.aspx>

Dose Fractionation Schedules

- 30 Gy in 3 fractions over 5 days

Physics Planning

- Type B or Monte Carlo algorithm is mandatory.
- Dose grid resolution on the final dose calculation must be ≤ 2 mm.
- The aim is to ensure the at least a portion of the dose fall off region from the prescription isodose occurs within disease with the aim of taking advantage of concentric isodose regions of differing dose per fraction to optimise the likelihood of immune priming with the RT. The choice of the area to irradiate will be at the discretion of the treating radiation oncologist taking into consideration the UK SABR Consortium Organs at Risk (OAR) constraints.

Table A: Contouring of normal tissue structures.

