Great Vessels	The great vessels (aorta and vena cava) will be contoured using mediastinal window to correspond to the vascular wall and all muscular layers out to the fatty adventitia. The great vessel should be contoured at least 10 cm above and below the extent of the PTV. For right sided lesions, the vena cava will be contoured, and for left sided lesions, the aorta will be contoured.
Oesophagus	The oesophagus should be contoured as a solid structure from the upper sphincter (cricoid level) down to the gastro-oesophageal junction using mediastinal windowing. The delineation limit is the outer wall of the oesophagus.
Heart and Pericardium	The heart will be contoured along with the pericardial sac using mediastinal windowing. The superior aspect is defined as the superior aspect of the pulmonary artery (as seen on coronal reconstruction of the CT) and the caudal border should be defined by the lowest part of the left ventricle's inferior wall that is distinguishable from the liver.
Chest Wall	The chest wall will be defined as the 2 cm rind of the ipsilateral hemi-thorax outside the thoracic cavity and contoured at least 5 cm above and below the PTV.

Target Coverage, Maximum Dose, Conformity Parameters and OAR Dose Constraints

- Target Coverage: Aim for the dose received by 95% and 99% of the PTV to be greater than 100% and 90% respectively ($D_{95} \geq 100\%$ and $D_{99} > 90\%$).
- Maximum Dose: This should ideally be within 110-140% (of the prescribed dose, 105-145% mandatory) and be located within the GTV. This is equivalent to prescribing to approximately the 70-95% isodose (relative to the maximum).
- Target Dose Conformity: Where possible the conformity constraints should be met (see Table B and C below).
- OAR dose constraints will be achieved for all patients (see Table D below).
- If the dose constraint for an OAR is not reached, the dose in the PTV will be reduced in order to meet the OAR constraint. Two approaches are possible:
- Reduced prescription dose: The prescribed dose can be reduced but to no less than 90% of the BED.
- Inhomogeneous PTV dose: In case of overlap of the PTV with OAR, the dose to the CTV (or ITV if applicable) can be maintained and the dose within the PTV may be reduced until the planned dose to the OAR meets the acceptable variation criteria for the OAR. The dose in 95% of the PTV should still at least be 80%.

Image Guidance for Treatment Verification and Delivery

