- CBCT (or 4D CBCT imaging where appropriate and available) and on-line correction prior to each fraction will be performed with manual adjustment under direct visualization of the tumour if required.
- The position of critical OAR will be checked, especially the spinal cord and any changes in anatomy.
- Repeat CBCT scans will be considered after correction prior to treatment delivery and again after treatment delivery if clinically indicated for additional verification.

[figure not shown]

Figure A: Recommended definition of a **central thoracic lesion**: a lesion within 2 cm in all directions of any mediastinal critical structure, including the bronchial tree, oesophagus, heart, brachial plexus, major vessels, spinal cord, phrenic nerve, and recurrent laryngeal nerve.

Table B: Prescription dose spillage (PDS) requirements for both lung and non-lung lesions

PTV (cc)	Body V _{100%} /PTV V _{100%}		
	Target	Tolerance	Minor Deviation
<20	1.20	<1.25	1.25-1.40
20-40	1.10	<1.20	1.20-1.30
>40	1.10	<1.15	1.15-1.20

Table C: Modified Gradient Index (MGI) requirements for lung sites

PTV (cc)	Body V _{50%} /PTV V _{100%}			Body-PTVExp20 D _{max} (Gy)
	Target	Tolerance	Minor Deviation	3# Tolerance ^{\$}
<20	7	9	9 – 11	<35.1
20-40	5.5	6.5	6.5 – 7.5	<37.8
40-60	5	6	6 – 7	<37.8
60-90	4	5	5 – 7	<37.8
>90	4	4.5	4.5 – 6.5	<37.8

Body-PTVExp20 D_{max} = Maximum point dose at least 2 cm from the PTV in any direction

^{\$}During CtE no lung plan exceeded the “Tolerance” level for Body-PTVExp20 D_{max} so the “Minor Deviation” level has been removed

Table D: OAR Dose Constraints

OAR parameter	Constraints for 3#		
	Optimal	Mandatory	
BrachialPlex	D _{0.5cc}	24Gy	26Gy
Bronchus_Prox	D _{0.5cc}	30Gy	32Gy
Chestwall	D _{0.5cc}	37Gy	-
	D _{30cc}	30Gy	-
GreatVes	D _{0.5cc}	-	45Gy
Heart+A_Pulm	D _{0.5cc}	26Gy	30Gy
Lungs-GTV (or ITV)	V _{20Gy}	-	10%
Oesophagus	D _{0.5cc}	-	25.2Gy
Skin	D _{0.5cc}	33Gy	-
	D _{10cc}	30Gy	-
SpinalCanal	D _{0.1cc}	18Gy	21.9Gy
	D _{1cc}	12.3Gy	-
Trachea	D _{0.5cc}	30Gy	32Gy

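### Table C's dose limit for points 2 cm or more outside the PTV (35.1 or 37.8 Gy) is above the trial's only prescription of 30 Gy, so it barely tests dose fall-off

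*Protocol*

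**What the plan says.** Section 4.2 (Table 1), section 7.2.6 (Table 7) and Appendix 3 give every patient in Parts A and B the same dose. Appendix 3 words it as "30 Gy in 3 fractions over 5 days". The only change of prescription that Appendix 3 permits is downward: "The prescribed dose can be reduced but to no less than 90% of the BED".

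On the hottest point of the plan, Appendix 3 says: "Maximum Dose: This should ideally be within 110-140% (of the prescribed dose, 105-145% mandatory) and be located within the GTV".

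Conformity is governed by Tables B and C, with the instruction "Where possible the conformity constraints should be met". Table B limits the ratio of body V100% to PTV V100%. Table C limits the ratio of body V50% to PTV V100%. Its last column (Body-PTVExp20 D_max, 3-fraction tolerance) limits the "Maximum point dose at least 2 cm from the PTV in any direction" to under 35.1 Gy in the smallest PTV class and under 37.8 Gy in the other four. A footnote explains why this column has no minor-deviation band: "During CtE no lung plan exceeded the" tolerance level. The protocol does not give the prescription used in CtE.

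For the organ limits in Table D the wording is firmer: "OAR dose constraints will be achieved for all patients".

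**The concern.** A limit on dose at a distance from the target is there to show that the dose has fallen off. To do that it has to lie below the prescribed dose. Here it lies above it, so recording the criterion as met says almost nothing about the plan.

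The column also sits badly with its neighbours. Table B treats any tissue outside the PTV that reaches 30 Gy as spillage, while Table C accepts a point above 30 Gy at 2 cm. Every other limit in the two tables is a ratio that follows the prescription. This column alone is in fixed Gy, so it becomes looser still whenever the dose is reduced to spare an organ.

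What is at stake is one planning check in a trial whose primary question is the safety of this radiotherapy with pembrolizumab. The toxicity definitions, the 3+3 rule and the analyses do not depend on it.

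**Working it through.** **Inputs, all from Appendix 3 unless noted**

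- Prescription: 30 Gy in 3 fractions, 10 Gy each (also section 4.2 and section 7.2.6).
- Table C limits: 35.1 Gy (PTV under 20 cc) and 37.8 Gy (larger PTVs).
- Plan maximum: 105–145% of prescription mandatory, 110–140% ideal.
- Lowest permitted prescription: 90% of the biologically effective dose (BED).

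**The plan's own figure.** The protocol states the limits in Gy only, with no percentage and no derivation. No percentage below 100% of 30 Gy gives either value.

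**Limit as a share of prescription**

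- 35.1 / 30 = 1.17, or 117%
- 37.8 / 30 = 1.26, or 126%

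**Plans that cannot fail.** The mandatory maximum runs from 1.05 × 30 = 31.5 Gy to 1.45 × 30 = 43.5 Gy, a band of 12.0 Gy. If the hottest point anywhere in the plan is below the limit, the column is met whatever the conformity.

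- PTV under 20 cc: (35.1 − 31.5) / 12.0 = 30% of the band
- Larger PTVs: (37.8 − 31.5) / 12.0 = 52.5% of the band

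On the ideal band (33.0 to 42.0 Gy, width 9.0 Gy) the shares are 2.1/9.0 = 23% and 4.8/9.0 = 53%. These are shares of a dose range, not of plans. A hotter plan fails only if more than 117% or 126% of prescription falls 2 cm or more outside the PTV.

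**After the largest permitted dose reduction.** Assumption: linear-quadratic BED = 3d(1 + d/(α/β)) with α/β of 10 or 3 Gy. The protocol gives no α/β.

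| α/β | BED at 30 Gy | 90% of BED | d per fraction | Total | 35.1 Gy is | 37.8 Gy is |
|---|---|---|---|---|---|---|
| 10 | 60 | 54 | 9.318 Gy | 27.95 Gy | 125.6% | 135.2% |
| 3 | 130 | 117 | 9.420 Gy | 28.26 Gy | 124.2% | 133.8% |

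**Where the figures might come from (illustration only).** The footnote points to plans from elsewhere. The table assumes three source prescriptions, none of which the protocol states.

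| Assumed source | Limits as % of source | Same % of 30 Gy |
|---|---|---|
| 45 Gy | 78% / 84% | 23.4 / 25.2 Gy |
| 54 Gy | 65% / 70% | 19.5 / 21.0 Gy |
| 60 Gy | 58.5% / 63% | 17.55 / 18.9 Gy |

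Both limits are round percentages of 54 Gy, which suggests values carried over from a higher dose, but that is inference. The finding does not need it.

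**The case against.** The strongest reply is that little depends on this column.

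- Tables B and C are to be met where possible, and meeting or missing this criterion triggers no action.
- The plan maximum is meant to lie in the GTV.
- Central lesions, meaning those within 2 cm of the mediastinal structures, are excluded. The organs at about this distance mostly have mandatory Table D limits stricter than 35.1 Gy: spinal canal 21.9, oesophagus 25.2, brachial plexus 26, heart 30, bronchus and trachea 32 Gy. Great vessels, at 45 Gy, are the exception.
- If the PTV is taken as a sphere of 5 to 120 cc, a plan exactly at the V50% tolerance has its 15 Gy surface about 1.2 to 2.0 cm outside the PTV. For example, at 20 cc the radius is 1.68 cm, and 1.68 × (9^(1/3) − 1) = 1.82 cm.
- Section 7.1.1 refers to external radiotherapy QA guidelines that may hold the intended value.

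Most of this stands, and it is why the weight is minor. It does not rescue the column. A criterion applied where possible should still separate good plans from poor ones. Volume ratios do not fix a point dose, so a small hot spot away from the target can pass both of them. Chest wall and skin, the tissues next to a pleural target, have optimal limits only in Table D. Nothing in the protocol rescales or overrides the Gy values.

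It is also true that a plan near the upper end of the mandatory band could in principle breach the limit. For that reason the column is called effectively, not strictly, non-functional.

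**Conclusion.** The point holds. The limit at 2 cm or more from the PTV is 117% or 126% of the only prescription in the trial, and both ratios are exact. The looser values after a permitted reduction (124–126% and 134–135%) rest on the assumed BED model. No estimate is made of the dose that real plans deliver at 2 cm, and no harm to patients is claimed. The result is one planning check that does not work, alongside others that do. It should be corrected, but the priority is low and no analysis or decision rule changes.

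**What to change.** Restate the Body-PTVExp20 D_max column as a percentage of the prescribed dose, below 100%, so that it follows any permitted reduction. Alternatively, give it in Gy scaled to 30 Gy. Ask radiotherapy QA for the source percentage before choosing the figure; the illustrative Gy values in the working are not proposals. If the footnote on CtE is kept, add the prescription to which that experience applies. Leave the absolute organ limits in Table D as they are.

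The cost is one query and one table column in the next amendment. Some plans with local spill may then be flagged as exceeding tolerance, which is the purpose of the check.

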12.4 Appendix 4 - Common Terminology Criteria for Adverse Events V5.0 (CTCAE)

The descriptions and grading scales found in the Common Terminology Criteria for Adverse Events (CTCAE) version 5.0 will be utilized for AR reporting. (<http://ctep.cancer.gov/reporting/ctc.html>)

1. Quick Reference

The NCI Common Terminology Criteria for Adverse Events is a descriptive terminology which can be utilized for Adverse Event (AE) reporting. A grading (severity) scale is provided for each AE term.

2. Components and Organization SOC

System Organ Class, the highest level of the MedDRA hierarchy, is identified by anatomical or physiological system, etiology, or purpose (e.g., SOC Investigations for laboratory test results). CTCAE terms are grouped by MedDRA Primary SOCs. Within each SOC, AEs are listed and accompanied by descriptions of severity (Grade).

3. CTCAE Terms

An Adverse Event (AE) is any unfavorable and unintended sign (including an abnormal laboratory finding), symptom, or disease temporally associated with the use of a medical treatment or procedure that may or may *not* be considered related to the medical treatment or procedure. An AE is a term that is a unique representation of a specific event used for medical documentation and scientific analyses. Each CTCAE v5.0 term is a MedDRA LLT (Lowest Level Term).

4. Definitions

A brief definition is provided to clarify the meaning of each AE term.

5. Grades

Grade refers to the severity of the AE. The CTCAE displays Grades 1 through 5 with unique clinical descriptions of severity for each AE based on this general guideline:

Grade 1 Mild; asymptomatic or mild symptoms; clinical or diagnostic observations only; intervention not indicated.

Grade 2 Moderate; minimal, local or non-invasive intervention indicated; limiting age-appropriate instrumental ADL*.

Grade 3 Severe or medically significant but not immediately life-threatening; hospitalization or prolongation of hospitalization indicated; disabling; limiting self-care ADL**.

Grade 4 Life-threatening consequences; urgent intervention indicated.

Grade 5 Death related to AE.

6. Activities of Daily Living (ADL)

*Instrumental ADL refer to preparing meals, shopping for groceries or clothes, using the telephone, managing money, etc. **Self-care ADL refer to bathing, dressing and undressing, feeding self, using the toilet, taking medications, and not bedridden.

12.5 Appendix 5 - Identification, Evaluation and Management of immune related events of clinical interest (irECIs)

ECI	Grade	Action to be taken	Supportive Care
Pneumonitis –	Grade 1 (Asymptomatic)	
 No action 	
 Intervention not indicated
	Grade 2	
 Withhold pembrolizumab, may restart if Grade 1 or resolved within 12 weeks Consider bronchoscopy and biopsy/BAL, ID Consult and frequent chest x-ray for monitoring. Conduct in person evaluation twice a week 	
 1-2mg/kg/day prednisone or equivalent. Symptoms grade 1 or less, initiate steroid taper for no less than 4 weeks. Permanently discontinue pembrolizumab if dose cannot be reduced to 10mg prednisone or less or equivalent per day within 12 weeks.
	Grade 3 and 4	
 Discontinue pembrolizumab Hospitalise patient Bronchoscopy with biopsy and/or BAL is recommended. 	
 methylprednisolone 125mg IV. Symptoms grade 1 or less initiate steroid taper for no less than 4 weeks 
 Prednisone 1 to 2 mg/kg/day or dexamethasone 4mg every 4 hours If IV steroids do not reduce initial symptoms within 48-72 hours treat with additional anti-inflammatory measures. At symptom relief discontinue anti-inflammatory and start steroid taper over 45-60 days. If symptoms worsen during this period refer to Section 7 and 8.

 1st episode - May increase dosing interval by one week in subsequent cycles 2nd episode of - Pneumonitis, permanently discontinue pembrolizumab if upon re-challenge patient develops Pneumonitis \geq Grade 2 			
Colitis	Grade 1 (Asymptomatic)	
 No action 	
 Intervention not indicated

–

	Grade 2 (For grade 2 diarrhoea that persists > 3 days)	
 Report overdose and liver toxicity ECIs within 24 hours Withhold pembrolizumab, may restart if Grade 1 or resolved within 12 weeks Symptomatic treatment 
 Consider GI consult & endoscopy to rule out colitis 	
 Prednisone 1-2mg/kg/day or equivalent Symptoms grade 1 or less, initiate steroid taper for no less than 4 weeks. Permanently discontinue pembrolizumab if dose cannot be reduced to 10mg or less of prednisone or equivalent per days within 12 weeks. If symptoms worsen or persist >1 week treat as grade 3.
--	---	--	--

	Grade 3	
 Withhold pembrolizumab Rule out bowel perforation Recommend gastroenterologist consult & biopsy with endoscopy 	
 methylprednisolone 125mg IV followed by prednisone 1 to 2 mg/kg/day or dexamethasone 4mg every 4 hours. Symptoms grade 1 or less initiate steroid taper for no less than 4 weeks. Taper 6-8 weeks in patients with diffuse or severe ulceration and/or bleeding If IV steroids do not reduce initial symptoms within 48-72 hours treat with additional anti-inflammatory measures. At symptom relief discontinue anti-inflammatory and initiate steroid taper over 45-60 days. If symptoms worsen during this period refer to Section 7 and 8.
	Grade 4	
 Discontinue pembrolizumab 	
 Manage as per grade 3
Endocrine – Hypo and hyperthyroidism	Grade 1 (Asymptomatic)	
 No action 	
 Intervention not indicated
	Grade 2 Hyperthyroidism and Grade 2- 4 Hypothyroidism	
 Monitor thyroid function until returned to baseline. Consider consultation with endocrinologist. Pembrolizumab can continue while on this treatment. 	
 Thyroid hormone and/or steroid replacement therapy. Hyper – non-selective beta blockers for initial therapy Hypo – thyroid hormone replacement therapy as per standard of care.
	Grade 3 Hyperthyroidism	
 Withhold pembrolizumab, may restart if Grade 1 or resolved within 12 weeks Rule out infection and sepsis. 	
 IV methylprednisolone 1-2mg/kg followed by prednisone 1-2mg/kg per day. Symptoms grade 1 or less initiate steroid taper for no less than 4 weeks. Replacement of appropriate hormones may be required. Permanently discontinue pembrolizumab if dose cannot be reduced to prednisone 10mg or less or equivalent per day within 12 weeks.
	Grade 4 Hyperthyroidism	
 Discontinue pembrolizumab 	
 Manage as per grade 3
Endocrine – Hypophysitis or other symptomatic endocrinopathy	Grade 1 (Asymptomatic)	
 No action 	
 Intervention not indicated
	Grade 2 – 4	
 Withhold pembrolizumab Rule out infection and sepsis. Monitor thyroid function until returned to baseline. Consider pituitary gland imaging Hypophysitis with clinically significant adrenal 	
 Prednisone 40mg p.o. or equivalent per day. Symptoms grade 1 or less initiate steroid taper for no less than 4 weeks. Replacement of appropriate hormones may be required. Permanently discontinue pembrolizumab if dose cannot be reduced to prednisone 10mg or less or equivalent per day within 12 weeks.

		
insufficiency and hypotension, dehydration, and electrolyte abnormalities (such as hyponatremia and hyperkalemia) constitutes adrenal crisis.
 
 Consider endocrinologist consult. 	
Type 1 Diabetes Mellitus and ≥ grade 3 hyperglycaemia	Type 1 Diabetes Mellitus and ≥ grade 3 hyperglycaemia	
 Hold pembrolizumab if new onset of diabetes or grade 3-4 hyperglycaemia with evidence of beta cell failure. Consultation with endocrinologist Consider islet cell antibodies and antibodies to GAD, IA-2 ZnT8 and insulin. 	
 Insulin replacement therapy is recommended for Type 1 diabetes mellitus and for Grade 3-4 hyperglycaemia associated with metabolic acidosis or ketonuria. Evaluate patients with serum glucose and a metabolic panel, urine ketones, glycosylated haemoglobin, and C-peptide.
Haematologic	Grade 1 (Asymptomatic)	
 No action 	
 Intervention not indicated
	Grade 2	
 Withhold pembrolizumab, may restart if Grade 1 or resolved within 12 weeks Consider Haematology consultation 	
 Prednisone 1-2mg/kg daily Permanently discontinue pembrolizumab if dose cannot be reduced to prednisone 10mg or less or equivalent per day within 12 weeks.
	Grade 3	
 Withhold pembrolizumab, may restart if Grade 1 or resolved within 12 weeks Recommend Haematology consultation 	
 IV methylprednisolone 125mg or Prednisone 1-2mg/kg p.o. (or equivalent) as appropriate. Permanently discontinue pembrolizumab if corticosteroid dose cannot be reduced to prednisone 10mg or less or equivalent per day within 12 weeks.
	Grade 4	
 Discontinue pembrolizumab Recommend Haematology consultation 	
 IV methylprednisolone 125mg or Prednisone 1-2mg/kg p.o. (or equivalent) as appropriate.
Hepatic – Drug induced Liver Injury (DILI). Please refer to Section 6 and 7 for definitions of (DILI)	Grade 1 (Asymptomatic)	
 No action 	
 Intervention not indicated
	Grade 2	
 Report liver toxicity ECIs within 24 hours, as detailed in Section 7.5.2. Withhold Pembrolizumab if AST or ALT >3.0 to 5.0 X ULN and/or total bilirubin is >1.5 to 3.0 X ULN Monitoring Liver function until values return to baseline 	
 0.5-1mg/kg/day methylprednisolone 125mg or oral equivalent. LFT grade 1 or less initiate steroid taper for no less than 4 weeks. Consider prophylactic antibiotics and resume pembrolizumab. Permanently discontinue pembrolizumab if dose cannot be reduced to prednisone 10mg or less or equivalent per day within 12 weeks.

			
 Permanently discontinue pembrolizumab for patients with liver mets who begin treatment with grade 2 elevation of AST or ALT and AST or ALT increase $\geq 50\%$ relative to baseline and lasts ≥ 1 week.
	Grade 3	
 Report liver toxicity ECIs within 24 hours, as detailed in Section 8.5.2. Discontinue pembrolizumab if AST or ALT $> 5.0 \times$ ULN and/or total bilirubin is $> 3.0 \times$ ULN Consider consultation and biopsy to establish aetiology 	
 High dose IV glucocorticosteroids for 24-48hours. Symptoms grade 1 or less initiate steroid taper for no less than 4 weeks 
 prednisone 1 to 2 mg/kg/day or dexamethasone 4mg every 4 hours. If serum transaminase levels do not decrease or symptoms worsen please refer to Section 7 and 8. Permanently discontinue pembrolizumab if dose cannot be reduced to prednisone 10mg or less or equivalent per day within 12 weeks.
	Grade 4	
 Report liver toxicity ECIs within 24 hours, as detailed in Section 8.5.2. Discontinue pembrolizumab 	
 Manage as per grade 3
Myocarditis ¹ ¶ Ensure that other causes of myocarditis are adequately evaluated to exclude other aetiologies	Grade 1 and 2	
 Withhold Pembrolizumab Consider Cardiology consult 	
 Prednisone 1 – 2 mg/kg or equivalent Restart treatment when symptoms are down to grade 1 and steroid dose is down to 10 mg or less of prednisone or equivalent 1-2mg/kg daily of prednisone or equivalent.
	Grade 3 and 4	
 Discontinue Pembrolizumab permanently Obtain Cardiology consult 	
 Prednisone 1 – 2 mg/kg or equivalent Permanently discontinue pembrolizumab
Neurologic	Grade 1 (Asymptomatic)	
 No action 	
 Intervention not indicated
	Grade 2	
 Consider withholding pembrolizumab Consider Neurology consult and biopsy for diagnosis. 	
 Consider 1-2mg/kg daily of prednisone as appropriate Permanently discontinue pembrolizumab if dose cannot be reduced to prednisone 10mg or less or equivalent per day within 12 weeks.
	Grade 3 and 4	
 Discontinue pembrolizumab Obtain Neurology consultation Consider biopsy for diagnosis. 	
 1-2mg/kg daily of prednisone or equivalent. If condition worsens consider IVIG or other immunosuppressive therapies Symptoms grade 1 or less, initiate steroid taper for no less than 4 weeks.
Ocular	Grade 1 (Asymptomatic)	
 No action 	
 Intervention not indicated
	Grade 2	
 Evaluation by ophthalmologist recommended 	
 Topical steroids – 1%prednisolone acetate suspension and iridocyclitics Permanently discontinue IF symptoms persist despite treatment.

	Grade 3	
 Evaluation by ophthalmologist recommended Withhold pembrolizumab & consider discontinuation. 	
 1-2mg/kg of prednisone daily. Symptoms grade 1 or less initiate steroid taper for no less than 4 weeks. Permanently discontinue pembrolizumab if dose cannot be reduced to prednisone 10mg or less or equivalent per day within 12 weeks.
	Grade 4	
 Evaluation by ophthalmologist recommended Permanently discontinue pembrolizumab 	Manage as per grade 3
Renal	Grade 1 (Asymptomatic)	
 No action 	
 Intervention not indicated
	Grade 2	
 Withhold Pembrolizumab 	
 1-2mg/kg of prednisone daily. Permanently discontinue pembrolizumab if dose cannot be reduced to prednisone 10mg or less or equivalent per day within 12 weeks.
	Grade 3 and 4	
 Discontinue Pembrolizumab Renal consultation and biopsy as appropriate 	
 1-2mg/kg of prednisone daily. Symptoms grade 1 or less initiate steroid taper for no less than 4 weeks.
Skin – Rash and pruritus	Grade 1 (Asymptomatic)	
 No action 	
 Intervention not indicated
	Grade 2	
 Symptomatic treatment 	
 Topical glucocorticosteroids or urea-containing cream in combination with oral anti-pruritics Treatment with oral steroids at PIs discretion
	Grade 3	
 Withhold Pembrolizumab Consider dermatology consult & biopsy for diagnosis. 	
 1mg/kg/day prednisone or equivalent or dexamethasone 4mg 4xdaily Symptoms grade 1 or less, initiate steroid taper for no less than 4 weeks. Permanently discontinue pembrolizumab if dose cannot be reduced to prednisone 10mg or less or equivalent per day within 12 weeks.
	Grade 4	
 Discontinue pembrolizumab Dermatology consultation Consider biopsy for diagnosis & clinical photographs 	
 Initiate steroids starting with 1-2mg/kg prednisone or equivalent.. Symptoms grade 1 or less, initiate steroid taper for no less than 4 weeks.
Skin – Dermatitis exfoliative, erythema multiforme, Stevens Johnson syndrome [§] , toxic epidermal necrolysis [§] .	Grade 1 (Asymptomatic)	
 No action 	
 Intervention not indicated
	Grade 2	
 Symptomatic treatment 	
 Topical glucocorticosteroids or urea-containing cream in combination with oral anti-pruritics. Treatment with oral steroids at PIs discretion
	Grade 3	
 Withhold Pembrolizumab 	
 1mg/kg/day prednisone or equivalent or dexamethasone 4mg 4xday.

§ If it is suspected that the patient has SJS or TEN, pembrolizumab should be withheld. The patient should be referred to a dermatologist for management. If SJS and TEN is confirmed, then pembrolizumab should be permanently discontinued."
		
 Consider dermatology consultation and biopsy for diagnosis. 	
 Symptoms grade 1 or less initiate steroid taper for no less than 4 weeks. Permanently discontinue pembrolizumab if dose cannot be reduced to prednisone 10mg or less or equivalent per day within 12 weeks.
	Grade 4	
 Report overdose and liver toxicity ECIs within 24 hours Permanently discontinue pembrolizumab Dermatology consultation Consider biopsy for diagnosis & clinical photographs 	
 Initiate steroids starting with 1-2mg/kg prednisone or equivalent.. Symptoms grade 1 or less, initiate steroid taper for no less than 4 weeks.

Other:
 
 Pericarditis Pancreatitis Any additional Grade 3 or higher event which the physician considers to be immune related 	Grade 2 or Grade 1 that do not improve with symptomatic treatment.	
 Report overdose and liver toxicity ECIs within 24 hours Withhold Pembrolizumab Consider biopsy for confirmation of diagnosis. 	
 Systemic corticosteroids may be indicated. If so: Treat with systemic corticosteroids at a dose of 1 to 2 mg/kg prednisone or equivalent once per day. When symptoms improve to Grade 1 or less, steroid taper should be started and continued over no less than 4 weeks. Permanently discontinue for inability to reduce corticosteroid dose to 10 mg or less of prednisone or equivalent per day within 12 weeks. Otherwise, Pembrolizumab treatment may be restarted and the dose modified as specified in the protocol
	Grade 3	
 Withhold Pembrolizumab 	
 Treat with systemic corticosteroids at a dose of 1 to 2 mg/kg prednisone or equivalent once per day. When symptoms improve to Grade 1 or less, steroid taper should be started and continued over no less than 4 weeks. Permanently discontinue for inability to reduce corticosteroid dose to 10 mg or less of prednisone or equivalent per day within 12 weeks. Otherwise, pembrolizumab treatment may be restarted and the dose modified as specified in the protocol
	Grade 4	
 Discontinue pembrolizumab 	
 Treat with systemic corticosteroids at a dose of 1 to 2 mg/kg prednisone or equivalent once per day.

12.6 Appendix 6 – Modified Response Evaluation Criteria in Solid Tumours (mRECIST) Criteria for Evaluating Response in Malignant Pleural Mesothelioma

The modified RECIST criteria were developed by Byrne and Novak (2004). Tumour thickness perpendicular to the chest wall or mediastinum should be measured in two positions at three separate levels on transverse cuts of CT scan.

In this protocol, mRECIST for MPM criteria will be used to assess response to therapy as follows:

1. mRECIST for MPM criteria will be used for tumour response evaluation in sites of disease outside the radiotherapy field by 2 cm above and 2 cm below the margins of the irradiated volume.
2. mRECIST for MPM criteria will be used for tumour response evaluation in sites of disease inside the radiotherapy field by 2 cm above and 2 cm below the margins of the irradiated volume.
3. As this is evaluating tumour responses of an immunotherapy drug, responses will need to be confirmed 4 – 6 weeks after the initial response imaging.

The sum of the six measurements defined a pleural unidimensional measure. Transverse cuts should be at least 1 cm apart and related to anatomical landmarks in the thorax that allow reproducible assessment at later time points, as shown above. If measurable tumour is present, transverse cuts in the upper thorax, above the level of division of the main bronchi are preferred. At reassessment, pleural thickness should be measured at the same position at the same level and by the same observer. This should not necessarily be the greatest tumour thickness at that level. Nodal, subcutaneous and other bidimensionally measurable lesions should be measured unidimensionally as per the RECIST 1.1 criteria. Unidimensional measurements are added to obtain the total tumour measurement.

Complete response (CR) was defined as the disappearance of all target lesions with no evidence of tumour elsewhere, and **partial response (PR)** was defined as at least a 30% reduction in the total tumour

measurement. A confirmed response required a repeat observation on two occasions 4 weeks apart. **Progressive disease (PD)** was defined as an increase of at least 20% in the total tumour measurement over the nadir measurement, or the appearance of one or more new lesions. Patients with **stable disease (SD)** were those who fulfilled the criteria for neither PR nor PD.

